14.3 Procedures for recording adverse events

- All Adverse events will be recorded in the CRF following consent.

14.4 Procedures for recording and reporting Serious Adverse Events

All serious adverse events will be recorded in the medical records and the CRF.

All SAEs (except those specified in section 14.5 as not requiring reporting to the Sponsor) must be recorded on a serious adverse event (SAE) form. The CI/PI or designated individual will complete an

SAE form and the form will be emailed to the R&I Office ([contact]) within 1 working day of becoming aware of the event.

14.5 Serious Adverse Events that do not require reporting

- Hospital Admission – admissions are very common in patients with kidney disease and therefore do not require reporting.

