Study A: POC-Cr will be assessed using the NovaMaxCreat and Epoc devices. Finger-prick capillary whole blood samples will be taken (0.05 uL for NovaMaxCreat and 0.9 uL for Epoc) using lancets by the research team. Venous serum creatinine for routine care (Isotope Dilution Mass Spectrometry (IDMS) Traceable Enzymatic assay) and ^{99m}Tc-DTPA glomerular filtration rate testing (where available) will be extracted from hospital laboratory databases. Participants not undergoing routine ^{99m}Tc-DTPA glomerular filtration rate testing will also have a 'eGFR filtration panel assessment – Beta-2-microglobulin, cystatin-C (processed by Synlab/ViaPath) and beta-trace-protein concentration (processed by Affinity laboratories), assessment on their venous blood sample.

Participants will be trained to use the POC-Cr device by the research team and time taken recorded and asked to perform one POC-Cr test.

In addition, the Epop Blood Analysis system, will also measure capillary potassium concentrations, which will be compared to serum potassium (taken from the venous blood sample for routine clinical care). This will be tested in the laboratory using the Roche Chemistry Analyser Cobas 8000.

Study B: Participants will be trained to use the POC-Cr device, NovaMaxCreat (NovaBio) by the research team and time taken recorded. Participants will be taught how to perform quality controls. All sample results will be digitally recorded by the device and downloaded after the device is returned. Participants will be asked to do one test at the hospital (with a simultaneous lab creatinine on site for validation), then to self-monitor four times per day (first thing in morning, midday, before evening meal/early evening, before bed) and each test recorded in a paper diary or electronically as desired. Details reported will include date and time of test, test success, device and non-device failures (test results, missed testing and reasons for missed test (e.g. forgot, did not want to test) and adverse events (e.g. pain or infection or prolonged injury after sampling, pre-syncopal or syncopal episode).

For participants who perform finger-prick testing for capillary blood glucose monitoring, both samples (creatinine using NovaMaxCreat and glucose using their usual device) can be taken from the same finger-prick test. However, participants will be advised to take the creatinine sample first.

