14 ADVERSE EVENTS AND INCIDENT REPORTING

14.1 Definitions of Adverse Events

Term	Definition
Adverse Event (AE)	Any untoward medical occurrence in a patient or study participant, which does not necessarily have a causal relationship with the intervention/treatment/procedure involved.
Serious Adverse Event (SAE).	Any adverse event that: 
 • results in death, • is life-threatening*, • requires hospitalisation or prolongation of existing hospitalisation**, • results in persistent or significant disability or incapacity, or • consists of a congenital anomaly or birth defect

*A life- threatening event, this refers to an event in which the participant was at risk of death at the time of the event; it does not refer to an event which hypothetically might have caused death if it were more severe.
 
** Hospitalisation is defined as an in-patient admission, regardless of length of stay. Hospitalisation for pre-existing conditions, including elective procedures do not constitute an SAE.
	

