14.2 Assessments of Adverse Events

Each adverse event will be assessed for severity, causality, seriousness and expectedness as described below.

Severity

Category	Definition
Mild	The adverse event does not interfere with the participant's daily routine, and does not require further procedure; it causes slight discomfort
Moderate	The adverse event interferes with some aspects of the participant's routine, or requires further procedure, but is not damaging to health; it causes moderate discomfort
Severe	The adverse event results in alteration, discomfort or disability which is clearly damaging to health

Causality

The assessment of relationship of adverse events to the procedure is a clinical decision based on all available information at the time of the completion of the case report form.

The following categories will be used to define the causality of the adverse event:

Category	Definition
Definitely:	There is clear evidence to suggest a causal relationship, and other possible contributing factors can be ruled out.
Probably:	There is evidence to suggest a causal relationship, and the influence of other factors is unlikely
Possibly	There is some evidence to suggest a causal relationship (e.g. the event occurred within a reasonable time after administration of the study procedure). However, the influence of other factors may have contributed to the event (e.g. the participant's clinical condition, other concomitant events).
Unlikely	There is little evidence to suggest there is a causal relationship (e.g. the event did not occur within a reasonable time after administration of the study procedure). There is another reasonable explanation for the event (e.g. the participant's clinical condition).
Not related	There is no evidence of any causal relationship.
Not Assessable	Unable to assess on information available.

Expectedness

Category	Definition
Expected	An adverse event which is consistent with the available information about the intervention/treatment/procedure in use in this study.
Unexpected	An adverse event which is not consistent with the available information about the intervention/treatment/procedure in use in this study*

* this includes listed events that are more frequently reported or more severe than previously reported

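### Section 14.5 waives the SAE form and the 1-working-day notice for every hospital admission, including one judged to be caused by finger-prick sampling

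*Protocol*

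**What the plan says.** Five parts of the protocol bear on this.

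- **Section 14.1** lists, among five SAE criteria, an event that "requires hospitalisation or prolongation of existing hospitalisation". Its footnote narrows this: "Hospitalisation for pre-existing conditions, including elective procedures do not constitute an SAE".
- **Section 14.2**: "Each adverse event will be assessed for severity, causality, seriousness and expectedness as described below". The causality scale has six categories: Definitely, Probably, Possibly, Unlikely, Not related and Not Assessable.
- **Section 14.4** puts every SAE in the medical records and the CRF. It then sets the reporting duty: "All SAEs (except those specified in section 14.5 as not requiring reporting to the Sponsor) must be recorded on a serious adverse event" form, emailed to the R&I Office within 1 working day of the team learning of the event.
- **Section 14.5** has one entry, hospital admission, with the reason that "admissions are very common in patients with kidney disease and therefore do not require reporting".
- **Section 3** (Study B) asks participants to report problems such as "pain or infection or prolonged injury after sampling, pre-syncopal or syncopal episode".

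Section 2.2 makes the safety of serial capillary testing a secondary objective of Study B. Section 6.1 opens Study B to people who have CKD and also to people who are only at risk of it through heart disease or diabetes.

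**The concern.** The reason in 14.5 is about background: people with kidney disease are often admitted for reasons unconnected with the study. That is a fair ground for sparing the sponsor a stream of uninformative reports. It is no ground for exempting an admission that the investigator attributes to the study procedure. The exemption nevertheless covers both, because it names a type of event and says nothing about its cause.

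What is at stake is how soon the sponsor hears of a serious event caused by sampling. Study B participants prick their own fingers several times a day, mostly at home. If one of them were admitted with an infected puncture site, the sponsor would want to know while others were still testing. The rule as written does not require anyone to tell it promptly.

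**Working it through.** The protocol gives no rate or threshold to reproduce, so no arithmetic applies. The check is to take one event through sections 14.1 to 14.5 in order.

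**Test case.** A Study B participant is admitted with an infection at a finger-prick site. No other SAE criterion is met.

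1. *Is it an SAE under 14.1?* Yes, through the hospitalisation criterion. The footnote does not remove it, because the infection is new and the admission is not elective.
2. *Is causality assessed under 14.2?* Yes. Suppose the grade is Definitely.
3. *Does 14.5 apply?* Yes. The event is a hospital admission, and the entry is not limited by cause, relatedness or expectedness.
4. *Does 14.4 require a form?* No, because 14.4 excepts whatever 14.5 lists.
5. *What remains?* Entries in the CRF and the medical records.

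Now change step 2 to Not related. Steps 3 to 5 come out the same. The causality grade therefore has no effect on whether an admission is reported.

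**Does the stated reason fit the scope?** Two passages suggest that it does not.

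| Provision | What it does | Consequence for 14.5 |
|---|---|---|
| 14.1 footnote | Takes admissions for pre-existing conditions and elective procedures out of the SAE definition | Many background kidney-disease admissions are already excluded. What 14.5 adds is largely admissions for new events, which is where procedure-related ones fall |
| 6.1, Study B criterion | Admits people who are only at risk of CKD | The reason given in 14.5 does not describe them, yet their admissions are exempt too |

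**Do other routes supply the prompt notice?**

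- Section 14.6 applies only once urgent safety measures have been taken.
- Section 14.7 concerns breaches of the protocol, which a correctly performed finger-prick is not.
- Section 14.8 requires incidents to be entered in the Trust's system. A sampling injury could qualify, but this is not an SAE form and is not tied to the causality grade.
- Section 15 has the Chief Investigator pass on concerns arising from monitoring, with no time limit.

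None of these replaces the 14.4 form for the test case.

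**The case against.** The strongest reply is that little is lost. Section 14.3 puts every adverse event in the CRF, 14.4 does the same for every SAE whether exempt or not, 14.2 has each graded for causality, and section 8 has Study B adverse events described and, where appropriate, quantified. The Study B safety objective can be met from those data. **This stands.** A reader might infer that procedure-related admissions would go unseen, or would never reach the sponsor. The documents do not support that: 14.5 waives a duty and forbids nothing, and the record is kept.

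A reader might also infer that a fatal, life-threatening or disabling event escapes reporting if it involves an admission. That goes too far. Such an event meets a separate 14.1 criterion and is arguably still reportable, although 14.5 does not say so.

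It is tempting, too, to size the problem by counting scheduled finger-pricks. That count measures exposure. Without a rate of infection, syncope or admission it says nothing about missed reports, and section 3 lets participants test more often or for longer, so it would not be an upper limit either. The infection and syncope in section 3 are examples of what to report; the protocol does not call them expected or serious.

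Two further points are fair. The SAE reporting flow chart under 14.7 is a figure not available to this review, and it might branch on relatedness. The study is also low risk: the procedure is a finger-prick, participation lasts one day or about one week, and people with bleeding disorders or severe skin conditions are excluded. These points limit the consequence and the certainty. They do not supply a reason for exempting an admission that the investigator has judged to be related.

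**Conclusion.** The point holds in limited form. On the visible text, 14.4 and 14.5 together waive the SAE form and the 1-working-day notice for every admission regardless of cause, and the reason given justifies this only for unrelated admissions. The consequence is delayed sponsor notice of a related admission, with no loss of the underlying data.

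No number of affected events can be derived from the protocol; serious events from finger-pricks are likely to be few. No endpoint, sample size or analysis depends on the rule. It should still be changed, because following it as written gives a worse safety result than the protocol's own causality assessment would allow.

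The conclusion assumes that the flow chart carries no relatedness condition. If it does, the flow chart and 14.5 disagree and the text still needs correcting.

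**What to change.** Reconcile 14.1, 14.2, 14.4 and 14.5 by limiting the exemption to admissions assessed under 14.2 as Unlikely or Not related to study procedures. All other admissions that meet the SAE definition (graded Possibly, Probably, Definitely or Not Assessable) go on the SAE form within the 14.4 timeline. Check that the flow chart says the same.

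The cost is one clause and a few extra reports. The causality grade is already required, so no new data are collected, and the intended relief from reporting background admissions is kept.

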14.6 Reporting Urgent Safety Measures

If any urgent safety measures are taken the CI/ PI shall immediately and in any event no later than 3 days from the date the measures are taken, give written notice to the relevant REC, Health Research Authority and R&I office of the measures taken and the circumstances giving rise to those measures.

14.7 Protocol deviations and notification of protocol violations

[figure not shown]
A deviation is usually an unintended departure from the expected conduct of the study protocol/SOPs, which does not need to be reported to the sponsor. The CI will monitor protocol deviations.

A protocol violation is a breach which is likely to effect to a significant degree –

- (a) the safety or physical or mental integrity of the participants of the study; or
- (b) the scientific value of the study.

The CI and R&I Office should be notified immediately of any case where the above definition applies during the study conduct phase.

Flow Chart for SAE reporting

14.8 Trust incidents and near misses

An incident or near miss is any unintended or unexpected event that could have or did lead to harm, loss or damage that contains one or more of the following components:

- a. It is an accident or other incident which results in injury or ill health.
- b. It is contrary to specified or expected standard of patient care or service.
- c. It places patients, staff members, visitors, contractors or members of the public at unnecessary risk.
- d. It puts the Trust in an adverse position with potential loss of reputation.
- e. It puts Trust property or assets in an adverse position or at risk.

Incidents and near misses must be reported to the Trust through DATIX as soon as the individual becomes aware of them.

A reportable incident is any unintended or unexpected event that could have or did lead to harm, loss or damage that contains one or more of the following components:

- a) It is an accident or other incident which results in injury or ill health.
- b) It is contrary to specified or expected standard of patient care or service.
- c) It places patients, staff members, visitors, contractors or members of the public at unnecessary risk.
- d) It puts the Trust in an adverse position with potential loss of reputation.
- e) It puts Trust property or assets in an adverse position or at risk of loss or damage.

15 MONITORING AND AUDITING

The Chief Investigator will ensure there are adequate quality and number of monitoring activities conducted by the study team. This will include adherence to the protocol, procedures for consenting and ensure adequate data quality.

The Chief Investigator will inform the sponsor should he/she have concerns which have arisen from monitoring activities, and/or if there are problems with oversight/monitoring procedures.

16 TRAINING

The Chief Investigator will review and provide assurances of the training and experience of all staff working on this study. Appropriate training records will be maintained in the study files

17 INTELLECTUAL PROPERTY

All intellectual property rights and know-how in the protocol and in the results arising directly from the study shall belong to KCL.

18 INDEMNITY ARRANGEMENTS

King's College London provides insurance for research involving human participants that covers legal liabilities arising from its actions or those of its staff (subject to policy terms and conditions).

KCH will provide NHS indemnity cover for negligent harm, as appropriate and is not in the position to indemnify for non-negligent harm. NHS indemnity arrangements do not extend to non-negligent harm and NHS bodies cannot purchase commercial insurance for this purpose; it cannot give advance undertaking to pay compensation when there is no negligence attributable to their vicarious liability. The Trust will only extend NHS indemnity cover for negligent harm to its employees; substantive and honorary, conducting research studies that have been approved by the R&D Department. The Trust cannot accept liability for any activity that has not been properly registered and Trust approved. Potential claims should be reported immediately to the R&I Office

19 ARCHIVING

During the study, all data will be kept securely and confidentially at the Renal Research office. After the study has ended, paper data recording sheets, the Trial Master file and patient consent forms will be archived at a long-term storage facility (Iron Mountain) for 5 years. Data spreadsheets will be encrypted, name and contact details removed, and stored on a private Renal research team folder with limited access.

20 PUBLICATION AND DISSEMINATION POLICY

The research team plans to disseminate the study research findings in the following settings:

- Conference presentation of study process and results at UK Kidney Week, American Society of Nephrology Conference or the European Renal Association conference and related Renal Conference
- Publication of results in a renal specific recognised impact journal.

22 APPENDICES

Appendix 1: PROTOCOL VERSIONS

Versions No	Version Date	Status
V 1.2	17 Mar 2020	Old
V 2.0	9 May 2020	Old
V 3.0	5 May 2022	Old
V 4.0	18 Oct 2022	Old
V.5.0	13 Mar 2023	Old
V 6.0	11 Aug 2023	Old
V 7.0	16 May 2024	Old
V 8.0	29 October 2024	Current
